5 STUDY ENROLLMENT AND WITHDRAWAL

Only adult subjects who meet the inclusion/exclusion criteria will be eligible for enrollment into this study. Ten subjects will be recruited, and five alternates who could replace subjects who drop out from the study for any unforeseen reason. The study population selected for this study includes healthy adult men and women ages 18 to 45, inclusive. The selection criteria are designed to exclude persons who might have medical conditions that could pose a safety risk and persons whose medical conditions might interfere with the objectives and results of the study.

Subjects may be recruited from the databases at the Center for Vaccine Development (CVD), by referral from another healthcare professional, and by advertisements local to the study center. Potential subjects who are interested in the study will be informed of the study and if they wish to participate, will receive additional study information, including an informed consent form. Each of the 10 subjects enrolled will be expected to complete the 6 procedure day sessions.

5.1 Subject Inclusion Criteria

Subjects are eligible for this study if they fulfill the inclusion criteria specified below:

- 1. Men or non-pregnant women of any ethnic background between the age of 18 and 45 years old.
- Subjects must be non-smokers (must have refrained from the use of nicotine-containing substances, including tobacco products (e.g., cigarettes, cigars, chewing tobacco, gum, patch or electronic cigarettes) over the previous 2 months and are not currently using tobacco products.
- 3. Provide written informed consent before initiation of any study procedures.
- 4. Available for follow-up for the planned duration of the study.
- 5. Able to communicate well with the investigators.
- 6. Able to adhere to the study protocol schedule.
- 7. Subjects who are within their ideal body weight (BMI>17 and \leq 28).
- Demonstrate comprehension of the protocol procedures and knowledge of study by passing (>70% correct responses) a written examination containing 20 multiple choice and true false questions covering all aspects of the study including the purpose, procedures, risks and benefits.
- 9. Subjects deemed to be healthy as judged by the Medically Accountable Investigator (MAI) and determined by medical history, physical examination, and medication history.

- 10. Negative urine drug screening test.
- 11. Have a normal blood pressure (systolic: 90-140 mmHg; diastolic: 50-90 mmHg) and heart rate (55-100 bpm).
- 12. Have normal screening laboratories for WBC, Hgb, platelets, sodium, potassium, chloride, bicarbonate, BUN, creatinine, ALT, AST and total bilirubin.
- 13. Have normal screening laboratories for urine protein and urine glucose.
- 14. Female subjects must be of non-childbearing potential (as defined as surgically sterile [i.e. history of hysterectomy or tubal ligation] or postmenopausal for more than 1 year), or if of childbearing potential must be non-pregnant at the time of enrollment and on the morning of each procedure, and must agree to use hormonal or barrier birth control such as implants, injectables, combined oral contraceptives, some intrauterine devices (IUDs), sexual abstinence, or a vasectomized partner.
- 15. Agrees not to participate in another clinical study during the study period.
- 16. Agrees not to donate blood to a blood bank throughout participation in the study and for at least 3 months after last procedure day.
- 17. Have a normal ECG.

5.2 Subject Exclusion Criteria

Subjects will be excluded for any of the following conditions/reasons:

- 1. Women who are pregnant, lactating breast feeding or have a positive serum pregnancy test at enrollment or on the morning of any procedure day.
- Smokers (current use or use over the previous 2 months of nicotine-containing substances, including tobacco products (e.g., cigarettes, cigars, chewing tobacco, gum, patch or electronic cigarettes).
- 3. Participation in any ongoing investigational drug trial or clinical drug trial.
- 4. Abnormal Vital signs, defined as:
 - Hypertension (systolic blood pressure >140 mm Hg or diastolic blood pressure >90 mm Hg) at rest on 2 separate days)
 - Heart rate <55 at rest on 2 separate days
 - Respiratory rate >20
- Temperature > 38.0°C (100.4°F) or symptoms of an acute self-limited illness such as an upper respiratory infection or gastroenteritis within 7 days of application of the transdermal fentanyl patch.
- 6. History of chronic obstructive pulmonary disease.
- 7. Active positive Hepatitis B, C, and HIV serologies.

- 8. Positive urine drug screening test.
- 9. Use of any prescription medication during the period 0 to 30 days or over-the counter medication (vitamin, herbal supplements and birth control medications not included) during the period 0 to 3 days before entry to the study.
- 10. Donation or loss of greater than one pint of blood within 60 days of entry to the study.
- 11. Any prior serious adverse reaction or hypersensitivity to fentanyl, naltrexone or naloxone or any of the inactive ingredients in the patch (alcohol, ethylene vinyl acetate-copolymer membrane and hydroxyethyl cellulose, polyester, silicone adhesive, isopropyl myristate, octyldodecanol, polybutene, polyisobutene, dimethicone NF, or polyolefin).
- 12. Have a diagnosis of schizophrenia or other major psychiatric diagnosis or mental illness (e.g. major depression).
- 13. Received an experimental agent (vaccine, drug, biologic, device, blood product or medication) within 1 month before enrollment in this study or expects to receive an experimental agent during the study.
- 14. Any condition that would, in the opinion of the Medically Accountable Investigator (MAI), place the subject at an unacceptable risk of injury or render the subject unable to meet the requirements of the protocol.
- 15. Inability to communicate or co-operate with the investigators.
- 16. History of consumption of alcohol within 24 hours prior to dose administration.
- 17. Within 72 hours prior to dosing, use of antihistamines or use of topical drugs at patch site.
- 18. Subject has an obvious difference in skin color between arms or the presence of a skin condition, open sore, scar tissue, tattoo, or coloration that would interfere with placement of test articles, skin assessment, or reactions to drug.
- 19. Use of monoamine oxidase inhibitors 21 days prior to study.
- 20. Failure to pass opioid dependence challenge test on each procedure day before application of the fentanyl patch. Each subject will be injected subcutaneously with naloxone HCI (0.8 mg injection) and will be observed for 45 minutes for signs and symptoms of opioid withdrawal.

6 STUDY PRODUCT

6.1 Study Product Description

6.1.1 Apotex (fentanyl) patch 25 µg/hour

Apotex (fentanyl) is a prescription transdermal patch that contains fentanyl which is a federally controlled substance (CII). Apotex (fentanyl) patches deliver fentanyl at a rate of 25 μ g/hour and are only for patients with chronic (around the clock) pain that is moderate to severe and expected to last for weeks or longer.

6.1.2 Mylan (fentanyl) patch 25 μg/hour

Mylan (fentanyl) is a prescription transdermal patch that contains fentanyl which is a federally controlled substance (CII). Mylan (fentanyl) patches deliver fentanyl at a rate of 25 μ g/hour and are only for patients with chronic (around the clock) pain that is moderate to severe and expected to last for weeks or longer.

6.1.3 Duragesic[®] (fentanyl) patch 25 μg/hour

Duragesic[®] is a prescription patch that contains fentanyl which is a federally controlled substance (CII). Duragesic[®] patches deliver fentanyl at a rate of 25 μ g/hour and are only for patients with chronic (around the clock) pain that is moderate to severe and expected to last for weeks or longer.

6.1.4 Naltrexone hydrochloride tablets, USP 50 mg

Naltrexone hydrochloride is an opioid antagonist which attenuates or reversibly blocks the effects of opioids. It is available as a prescription medication and is used to treat opioid addiction.

6.2 Formulation, Packaging, and Labeling

6.2.1 Apotex (fentanyl) patch 25 µg/h

Active ingredient (in each patch): Fentanyl, 25 µg delivered per hour. In addition to the active ingredient (fentanyl), the following inactive ingredients are present in the patch: polyester film (backing layer), isopropyl myristate, octyldodecanol, polybutene and

polyisobutene (adhesive matrix), and polyester protective release liner. This product should be stored below 25°C (77°F).

6.2.2 Mylan (fentanyl) patch 25 µg/h

Active ingredient (in each patch): Fentanyl, 25 μ g delivered per hour. In addition to the active ingredient (fentanyl), the following inactive ingredients are present in the patch: Dimethicone NF and silicon adhesive and polyolefin film backing. This is a matrix type patch, manufactured by Mylan Pharmaceuticals Inc. This product should be stored below 25°C (77°F).

6.2.3 Duragesic[®] (fentanyl) patch 25 μg/h

Active ingredient (in each patch): Fentanyl, 25 μ g delivered per hour. In addition to the active ingredient (fentanyl), the following inactive ingredients are present in the patch: alcohol, ethylene vinyl acetate-copolymer membrane and hydroxyethyl cellulose, polyester film backing, silicone adhesive. This is a matrix type patch, manufactured by ALZA and distributed by Janssen pharmaceutics. This product should be stored below 25°C (77°F).

6.2.4 Naltrexone hydrochloride tablets, USP 50 mg

Active ingredient (in each tablet): Naltrexone hydrochloride, USP 50 mg. In addition to the active ingredient (naltrexone hydrochloride), the following inactive ingredients are present in the patch: crospovidone, hypromelloses, lactose monohydrate, magnesium stearate, microcrystalline cellulose, polyethylene glycols, polysorbate 80, silicon dioxide, titanium dioxide, ferric oxide yellow and ferric oxide red. This is an oral tablet, manufactured by Covidien Ltd. and distributed by Mallinckrodt Pharmaceuticals. This product will be stored at room temperature, 20 to 25°C (68 to 77°F).

6.2.5 Naloxone hydrochloride injection, USP 0.4 mg/ml

Active ingredient (in each injection): Naloxone hydrochloride, USP 0.4 mg/ml single dose ampoule for intravenous, intramuscular or subcutaneous use. This product will be stored at room temperature, 20 to 25°C (68 to 77°F).

7 PHARMACOKINETICS AND STATISTICAL CONSIDERATIONS

7.1 Study Hypotheses

Due to differences in inactive ingredients between reference and generic fentanyl transdermal patches the release rate of fentanyl may differ from these patches upon exposure to heat. As a result, in this study the influence of standardized heat application (two heat periods) on the pharmacokinetics (PK) parameters of fentanyl will be studied after using Duragesic[®] (reference), Apotex (fentanyl) (generic), and Mylan (fentanyl) (generic) transdermal patches.

The primary analysis will be to determine whether heat differentially impacts fentanyl serum concentrations among Duragesic[®] (reference), Apotex (fentanyl), and Mylan (fentanyl) transdermal patches. We will test the null hypothesis (H₀) that the coefficient for the patch-by-heat interaction equals zero, adjusting for time.

7.2 Pharmacokinetics (PK) Analyses

Fentanyl concentrations will be measured in serum samples collected from each subject from the opposite arm to which the fentanyl system will be applied. Blood samples (approximately 5 mL) will be collected during each procedure day, 15 min before patch application and then at 1:00, 10:00, 10:55, 11:05, 11:15, 11:25, 11:35, 11:45, 12:00, 13:00, 14:00, 16:00, 17:00, 17:55, 18:05, 18:15, 18:25, 18:35, 18:45, 19:00 20:00, 21:00 and 22:00 hr post-patch application. The fentanyl PK parameters to be estimated using non-compartmental analysis (NCA) after each system application are: maximum serum concentration (Cmax) at different time intervals; 0-11, 0-19, 0-22, 11-12, 12-18, 18-19 and 19-22 hr; apparent elimination rate constant (k); apparent half-life (t1/2), calculated as 0.693/k; AUC of the serum concentration–time at different time intervals; 0-11, 0-19, 0-22, 11-12, 12-18, 18-19 and 19-22 hr determined by the linear trapezoidal method; and AUC value extrapolated to infinity (AUCinf), calculated as the sum of AUC₂₂ and the area extrapolated to infinity: AUCinf = AUC₂₂ + C₂₂/k where C₂₂ would be the last quantifiable concentration. All NCA analyses will be conducted using Phoenix® WinNonlin[®] 6.3 (Pharsight, a Certara Company, CA).

7.3 Final Analysis Plan

The main objective of this study is to investigate the influence of heat application on the PK parameters of fentanyl after using reference and generic patch products. The primary PK parameters to be compared are 1) Cmax, before and after heat application and 2) AUC before and after heat application consistent with similar PK studies [4, 5, 7, 8, 16-22]. Analysis of variance (ANOVA) followed by post-hoc Bonferroni test will be used for comparing the differences in the means of the PK parameters and significant differences will be declared at p < 0.05. The statistical comparisons will be conducted as follow:

Three pair-wise comparisons between the patches (Apotex v Mylan; Apotex v Duragesic[®]; and Mylan v Duragesic[®]) will be performed using the results of a three-way repeated-measures ANOVA. The model will include time, type of patch (e.g., Apotex or Mylan), application of heat (yes or no), and interaction between patch and application of heat. The time term comprises multiple indicator variables for maximum model flexibility to perform the comparison at different time points specified above. We will test the null hypothesis that the coefficient for the patch-by-heat interaction equals zero, adjusting for time.

If fentanyl concentrations are found to be non-normally distributed, then we will examine Box-Cox transformations (e.g., log, square-root, etc.) that can achieve normality. If no transformation can achieve normality, then we will use permutation tests to compute empirical p-values, and we will use the bootstrap to compute standard errors and confidence intervals that account for within-person correlation.

A secondary analysis will assess the effects of heat and time on fentanyl within a patch. Specifically, the ANOVA will also include interaction terms of time with patch and heat, and a three-way interaction between time, heat, and patch. Inclusion of the three-way term allows the effects of heat on fentanyl to differ by patch. Testing the time-by-heat interaction, separately for each patch, using the same procedure outlined above produces estimates of intra-procedure effects.

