4 STUDY DESIGN

This is an open-label, non-placebo controlled pharmacokinetic (PK) assessment study. The study will consist of six-procedure days (10 subjects) with at least two weeks between procedure days. The half-life of fentanyl is approximately 24 hours. Hence, 7 days (i.e. 5 half-lives) will be sufficient for >95% of fentanyl to be eliminated from the body. Each of the 10 subjects will be enrolled to complete all six procedure days (Procedure Days 1 to 6). The study is open label and not blinded, because PK assessment is not subject to participant and/or observer bias. After each procedure session (procedure day) is completed, the available safety data will be reviewed by an Independent Safety Monitor (ISM) to determine whether or not to proceed to the next procedure day.

The six procedures days are as follows:

Procedure Day 1: An **Apotex** (fentanyl) patch will be applied without heat for 11 hours, then a theratherm® heating pad will be applied over it (see details in Manual of Procedures) and set to induce a skin temperature of $42.0 \pm 2^{\circ}$ C for 1 hour then removed, and the patch will be kept on for another 7 hours (patch will be applied for a total of 19 hours), then it will be removed. Each subject will receive a naltrexone hydrochloride 50 mg oral tablet 12 ± 1 hour and shortly prior to patch application and then every 12 ± 1 hour for 8 additional doses, then one dose every 24 ± 2 hours for two more doses. A total of twelve 50 mg oral doses of naltrexone will be administered.

Procedure Day 2: An **Apotex** (fentanyl) patch will be applied without heat for 18 hours, then a theratherm® heating pad will be applied over it and set to induce a skin temperature of $42.0 \pm 2^{\circ}$ C for 1 hour, then the patch and the heating pad will both be removed (patch will be applied for a total of 19 hours). Each subject will receive a naltrexone hydrochloride 50 mg oral tablet 12 \pm 1 hour and shortly prior to patch application and then every 12 ± 1 hour for 8 additional doses, then one dose every 24 ± 2 hours for two more doses. A total of twelve 50 mg oral doses of naltrexone will be administered.

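### For the three patch pairs within one PK parameter, plain Bonferroni is stricter than 5% family-wise error requires; Holm, or a joint interaction test followed by pairs at 0.05, is a cheap improvement

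*Combined protocol and SAP*

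**What the plan says.** The multiplicity rule stands in the combined protocol and SAP, section 7.3: "Analysis of variance (ANOVA) followed by post-hoc Bonferroni test will be used for comparing the differences in the means of the PK parameters", with "significant differences will be declared at p < 0.05". The same section plans "Three pair-wise comparisons between the patches", taken from a three-way repeated-measures ANOVA. Its hypothesis reads: "We will test the null hypothesis that the coefficient for the patch-by-heat interaction equals zero, adjusting for time".

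Four things are left open:
- the Bonferroni divisor;
- whether the pairs are tested only if the ANOVA is significant;
- whether the tests are two-sided;
- how one interaction coefficient is to stand for three patches, which need two.

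The separate SAP file covers the in vitro–in vivo correlation and adds nothing on this point.

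On size, section 4 says "Each of the 10 subjects will be enrolled to complete all six procedure days", and section 5 provides "five alternates who could replace subjects who drop out from the study for any unforeseen reason". The text available gives no SD, effect size or power.

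**The concern.** The study asks whether heat affects one patch more than another. Naming the patch that differs is a pairwise claim, so pairwise power matters. Three patches give a closed set of three comparisons in which any two equalities force the third. Bonferroni ignores that structure and guards against a situation that cannot arise, namely exactly two true nulls beside one real difference. With 10 subjects, power given up without need is worth recovering if the change is cheap and the 5% limit is kept.

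**Working it through.** **Inputs.** From section 7.3: level 0.05 (taken as two-sided) and three pairs. From section 4: 10 subjects, each with all three patches. Assumed: a divisor of 3, and a patch difference in heat effect of 0.4 to 1.6 SDs of the paired difference (d). The plan has no power figure to reproduce.

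**Step 1: what Bonferroni spends.** The per-pair level is 0.05/3 = 0.0167. The true nulls can number three, one or none, never two. If exactly one is true, the family-wise error is just that pair's level, about 1.7%, against an allowance of 5%.

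**Step 2: two rules that use the allowance.**
- *Holm.* Compare the ordered p-values with 0.05/3 = 0.0167, 0.05/2 = 0.025 and 0.05, stopping at the first failure. The first step is Bonferroni's own, so Holm never rejects less, and the chance of at least one rejection is unchanged.
- *Gated rule.* Test the joint 2-df interaction at 0.05 and, if significant, each pair at 0.05. Any two pairwise nulls together equal the joint null, so the closed-testing family is the joint null plus the three single ones. Error stays at or below 5% if every test is valid.

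**Step 3: size under equal variances.** Simulation: 10 subjects by 3 patches, one heat effect per subject and patch, normal errors, pooled error, F with 2 and 18 df.

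Family-wise error with no differences was 4.28% for Bonferroni, 4.24% for Bonferroni behind a significant F test, and 5.1% for the gated rule (nominal 5%, simulation error). With one patch differing, it was about 1.7% for Bonferroni and 3.6% to 5.1% for the gated rule.

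Power for a differing pair, one patch differing from two equal ones, is below. The SD of a paired difference is √2 times the residual SD, so d is the residual-SD figure divided by 1.414.

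| Residual SDs | d | Bonferroni | Holm | Gated | Gain, Holm | Gain, gated |
|---|---|---|---|---|---|---|
| 0.75 | 0.53 | 19.8% | 21.4% | 26.7% | 1.6 | 6.9 |
| 1.0 | 0.71 | 37.3% | 40.0% | 47.7% | 2.7 | 10.4 |
| 1.25 | 0.88 | 57.1% | 60.6% | 69.1% | 3.5 | 12.0 |
| 1.5 | 1.06 | 75.9% | 79.4% | 85.6% | 3.5 | 9.7 |
| 2.0 | 1.41 | 95.9% | 97.1% | 98.6% | 1.2 | 2.7 |
| 2.25 | 1.59 | 98.7% | 99.3% | 99.7% | 0.6 | 1.0 |

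Power to find any difference does not move with Holm and rises by at most about 4.5 points with the gated rule (for example 51.3% to 55.6% at 1.0 residual SD). If the patches are equally spaced instead, the gated rule gains at most about 5 points for the extreme pair and up to about 19 for an adjacent pair.

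**Step 4: does a gate hurt Bonferroni?** With the pooled F test, requiring significance first costs at most about 0.2 points. The loss comes from the 0.05/3 threshold.

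**Step 5: unequal variances.** With pooled error and assumed SDs of 1, 1, 3, the gated rule reaches 7.3% with no differences and about 9.7% with one patch differing; Bonferroni gives 5.9% and 4.4%. With SDs of 1, 1, 2 the figures are 6.1% and 7.9%, against 5.2% and 3.1%. Holm shares the weakness when both real differences are large, because its last step then also tests the null pair at 0.05 with the pooled error.

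A multivariate 2-df test with pair-specific paired contrasts brings the gated rule back to 4.6% with no differences and at most 5.1% with one patch differing. Its gain over paired Bonferroni, under equal variances, is 39.6% to 48.1% at d = 0.8 and 60.4% to 70.1% at d = 1.0. This gate has fewer error df (2 and 10 − 2 = 8), so the gain in finding any difference should not be carried over to it.

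**Step 6: scope.** Section 7.3 names two primary parameters: "The primary PK parameters to be compared are 1) Cmax, before and after heat application and 2) AUC before and after heat application". Section 7.2 lists "maximum serum concentration (Cmax) at different time intervals; 0-11, 0-19, 0-22, 11-12, 12-18, 18-19 and 19-22 hr", and the same seven intervals for AUC. Running the gated rule on two uncorrelated parameters gives 1 − 0.95² = 9.75% (simulated 9.7%); at correlation 0.8 it is 8.1%, and at 0.95 it is 6.6%. The 5% limit therefore holds per parameter and interval. Bonferroni with a divisor of 3 has the same gap.

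**The case against.** Bonferroni is valid, standard, needs no joint test and yields simultaneous confidence intervals directly. In a 10-subject PK study, keeping it is defensible. The alternatives also make more false claims on a truly null pair, even if within 5%. All of this stands, and it makes the point an improvement and not the correction of an error. It does not remove the point, because Holm also needs no joint test and loses no rejection that Bonferroni makes.

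The divisor is a fair objection too. If the sponsor means Bonferroni to cover Cmax, AUC or the intervals as well, the family is larger than three pairs, and relaxing it would remove protection that the three-patch argument does not replace. The point depends on a divisor of 3.

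A reader might infer that the plan pays for multiplicity twice, first through a significant ANOVA and then through Bonferroni. The documents do not support that: section 7.3 gives an order of analyses and states no gate, and a pooled F gate would cost almost nothing (step 4).

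**Conclusion.** The point holds as a cheap efficiency gain. For the three pairwise patch-by-heat comparisons within one parameter, Bonferroni at 0.05/3 is stricter than a 5% family-wise error requires. Under the assumptions of step 3 and d from 0.4 to 1.6, the gain for a differing pair is about 0.5 to 4 points with Holm and about 1 to 12 with the gated rule.

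A reader might take a gain of about 11 points as a general figure. It is not: it lies near the peak of one assumed pattern, and the documents supply no SD or effect size to place the trial there. Nor may one infer that either rule holds the whole trial's error at 5%. Heat was also reduced to one effect per subject and patch, so the planned model on all time points would need its own covariance assumptions.

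**What to change.** In section 7.3, define the family as the three pairwise patch-by-heat interaction contrasts within one PK parameter, and replace Bonferroni with Holm at a two-sided family-wise 5%. Holm needs only valid pairwise p-values, so use pair-specific paired contrasts if unequal variability between patches is a concern.

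Alternatively, state that the joint 2-df patch-by-heat interaction is tested at 0.05, that each pairwise interaction contrast is tested at two-sided 0.05 only if it is significant, and that no pairwise claim is made otherwise. This version must name an error term that does not assume sphericity, such as a multivariate 2-df test with pair-specific paired contrasts.

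Holm costs a sentence or two. The gated version also needs the joint test written out, since section 7.3 now speaks of a single coefficient. Either way, simple simultaneous confidence intervals are lost and false claims on a truly null pair may rise from about 1.7% to at most 5%. Say separately how alpha is handled across Cmax, AUC and the intervals. If Bonferroni is kept, state its divisor.

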2.2 Rationale

The objective of this proposal is to conduct in vivo studies to compare the influence of heat on fentanyl drug release from FDA approved TDDS products (reference e.g. Duragesic[®], versus generic products e.g. Apotex and Mylan transdermal patches) that have different inactive ingredients. While there is data in the literature for heat effect on different active pharmaceutical ingredients (API's), specifically reference listed drugs (RLD), from exposure to heating blankets, sauna, hot showers, exercising, there is no head to head comparisons for heat effect on RLD versus generic drugs. This study will help support policy development for characterization of heat effects for future generic applications. Furthermore, if in-vitro in-vivo correlation (IVIVC) can be established, then in vitro studies can be used for generic applications in the future, which would mitigate

exposure of human beings to out of label studies. This approach will help ensure that patients would not be subjected to additional risks if they use a generic TDDS rather than its respective reference product.

Fentanyl was selected for this study because it is a drug with significant and well characterized heat effect studies in the literature, and for which an antidote exists. Fentanyl has the most variability available in terms of generic transdermal systems with different formulations that are approved and already on the market. This study will provide data that could potentially help us determine if one formulation/adhesive is more prone to heat effect/changes in delivery compared to another. Furthermore by demonstrating IVIVC then in vitro studies can be conducted on generic fentanyl transdermal patches in the future without the need to subject human volunteers to additional testing. To mitigate the potential risk of a higher absorption of fentanyl through the skin, the lowest strength patch is being used in this study (25 µg/hr).

Duragesic® versus Apotex (fentanyl) and Mylan (fentanyl) transdermal patches

	Duragesic [®]	Apotex (fentanyl) patch	Mylan (fentanyl) patch
Inactive ingredients	Alcohol, ethylene vinyl acetate-copolymer	Isopropyl myristate, octyldodecanol, polybutene	Dimethicone NF, polyolefin film backing,
	membrane and hydroxyethyl cellulose, polyester film backing, silicone adhesive	and polyisobutene adhesive	silicon adhesive
TDDS type	Matrix	Matrix	Matrix
Manufacturer	Janssen	Apotex	Mylan

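### The primary patch-by-heat null is written as one coefficient where three patches give two, and section 7.3 does not say which of its three pairs carry the conclusion

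*Combined protocol and SAP*

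**What the plan says.** All references are to the combined protocol and SAP. The separate SAP deals with in vitro–in vivo correlation and adds nothing on this point.

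- **Question (7.1).** The primary analysis asks "whether heat differentially impacts fentanyl serum concentrations among Duragesic[®] (reference), Apotex (fentanyl), and Mylan (fentanyl) transdermal patches".
- **Null (7.1, repeated in 7.3).** "We will test the null hypothesis (H₀) that the coefficient for the patch-by-heat interaction equals zero, adjusting for time".
- **Model (7.3).** A three-way repeated-measures ANOVA with time, type of patch, "application of heat (yes or no), and interaction between patch and application of heat".
- **Comparisons (7.3).** "Three pair-wise comparisons between the patches (Apotex v Mylan; Apotex v Duragesic[®]; and Mylan v Duragesic[®]) will be performed". None is ranked or named as primary.
- **Error control (7.3).** "Analysis of variance (ANOVA) followed by post-hoc Bonferroni test will be used for comparing the differences in the means of the PK parameters". The significance level is set at 0.05. No divisor, family or sidedness is given.
- **Purpose (2.2).** The section identifies a lack of direct reference-versus-generic data on heat. It also says: "This approach will help ensure that patients would not be subjected to additional risks if they use a generic TDDS rather than its respective reference". It adds that the data could show whether one formulation or adhesive is more sensitive to heat than another.

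**The concern.** The singular coefficient does not match a three-product question. A reader of 7.1 and 7.3 cannot tell whether the primary conclusion rests on a joint test of the interaction, on any one of three pairs, or on the two pairs that involve Duragesic. These rules can give different answers on the same data: the overall test, or Apotex v Mylan alone, can be significant while neither generic is shown to differ from the reference.

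The undefined family matters as well. If Bonferroni is spread over three pairs, the generic-versus-generic pair draws on the same alpha as the two reference comparisons that section 2.2 puts foremost. If Bonferroni is not meant for these contrasts, the three tests may be uncontrolled. Either way, the choice could be made after the data are seen.

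**Working it through.** **Inputs from the documents.** Three patches and two heat levels (7.1, 7.3); 10 subjects completing all six procedure days (Protocol Summary); p < 0.05 and Bonferroni (7.3). The text supplied for review gives no power, target effect or variance, so there is no figure of the plan's own to reproduce.

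**Assumed.** Two-sided tests; one heat-effect contrast per subject and patch; effect d in units of the SD of the within-subject difference between two patches.

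**1. Counting.** Interaction df = (3 − 1)(2 − 1) = 2. The design-matrix rank confirms this: 4 with main effects only, 6 with the interaction. Pairs = 3 × 2 / 2 = 3.

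**2. Alpha, if Bonferroni covers the contrasts.**
- Three pairs: 0.05/3 = 0.0167 each. Two reference contrasts: 0.05/2 = 0.025 each.
- Loss per reference test: 1 − 0.0167/0.025 = one third.
- If Cmax and AUC share the family: 0.05/6 = 0.0083 v 0.05/4 = 0.0125, again one third.

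**3. Power for one reference contrast.** Noncentral t with noncentrality d√n; at d = 1.0 this is √10 = 3.16.

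| Error df | Power at 0.0167 | Power at 0.025 | d for 80% power (0.0167 v 0.025) |
|---|---|---|---|
| 18 (pooled ANOVA error) | 69.6% | 75.7% | 1.11 v 1.05 |
| 9 (paired test) | 60.4% | 68.2% | 1.22 v 1.14 |

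With 18 df the cost is 75.7 − 69.6 = 6.1 points. With 9 df it is 68.2 − 60.4 = 7.8 points.

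**4. Familywise error, if Bonferroni does not cover the contrasts.** Three correlated pairs each at 0.05 with no preceding test: studentized range for three groups, evaluated at √2 × t(0.975). Result: 11.3% (9 df), 11.8% (18 df), 12.2% (large df).

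**5. Alternative procedures at d = 1.0** (simulation, 40,000 trials, 10 subjects, 18 error df).

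| Procedure | Power, true generic v Duragesic difference |
|---|---|
| Bonferroni, three pairs | 69–70% |
| Bonferroni, two reference contrasts | 76% |
| Holm, two reference contrasts | 76% (one generic differs), 81% (both differ) |
| 2-df test at 0.05, then each pair at 0.05 | 80–81% |

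Familywise error under the global null is 4.6% for the two-contrast Bonferroni family and about 5% (simulated 0.051) for the last row. With three groups, that last procedure is a closed test.

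**6. How often the candidate rules disagree.** The last two columns give the share of trials where the 2-df test is significant and no reference contrast is.

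| Truth | Reference contrasts at 0.0167 | Reference contrasts at 0.025 |
|---|---|---|
| One generic differs, d = 0.8 | 19% | 13% |
| One generic differs, d = 1.0 | 16% | 10–11% |
| One generic differs, d = 1.2 | 9% | 6% |
| Generics on opposite sides of Duragesic, ±0.5 or ±0.6 | about 41% | about 32% |

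**The case against.** Four points stand on the other side.

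- **A hierarchy is implied.** ANOVA followed by a post-hoc test ordinarily means an overall interaction test and then pairs. Also, the patch term in 7.3 is illustrated with two products only, which could mean a separate model per pair; one coefficient would then be correct. The first reading is natural but unwritten, and no 2-df test is specified. The second gives three primary nulls and still no rule for choosing among them.
- **Apotex v Mylan has a stated rationale.** A reader might infer that the trial exists only for the reference comparisons, so that alpha spent on this pair buys nothing. The documents do not support that: section 2.2 has a formulation-versus-formulation interest, and 7.1 asks about differences among all three products.
- **The 0.0167 is inferred.** A reader might take it as the plan's threshold. The plan writes no divisor, and it attaches Bonferroni to means of PK parameters while 7.1 poses the interaction on serum concentrations.
- **The power loss comes from single-step Bonferroni, not from having a third pair.** The closed procedure keeps all three pairs and does at least as well as the two-contrast Bonferroni.

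The disagreement figures also need care. When the generics lie on opposite sides of Duragesic, Apotex and Mylan truly differ, so a significant overall test is correct. Much of the disagreement also remains at 0.025. It shows that the decision rule must be named. It does not show that any one test is wrong.

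**Conclusion.** The point holds as one of specification. The null is miscounted (one coefficient for two), the Bonferroni family is undefined, and no contrast is named as carrying the conclusion. The count rests on the documents alone, given a single three-patch model.

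The size depends on which reading applies: about 6 points of power per reference contrast at an assumed d = 1.0 with 18 error df, or a familywise error of about 12% if the pairs are unadjusted and ungated. Both are illustrative. They use assumed effects and one contrast per subject and patch, not the planned time-indicator model. A reader might conclude that the trial cannot answer its question; nothing here supports that. The model and data suffice, and the gap is in the stated rule.

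**What to change.** Amend 7.1 and 7.3 before analysis:

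1. State the primary null as the 2-df joint patch-by-heat interaction: both the Apotex-minus-Duragesic and the Mylan-minus-Duragesic heat effects are zero.
2. Name those two contrasts as carrying the primary conclusion, controlled jointly at two-sided 0.05, for example by Holm or Dunnett over the two.
3. Keep Apotex v Mylan as a secondary or later hierarchical comparison, reported with an estimate and interval.
4. State the multiplicity family, including whether Cmax and AUC share it.

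If the investigators want all three pairs confirmatory, replace single-step Bonferroni with the closed procedure: the 2-df test at 0.05, then, only if it is significant, each pair at 0.05. In the illustration this gives about 80% power with familywise error near 0.05.

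The cost is wording only, with the same model, subjects and data. Under the first option, Apotex v Mylan has weaker confirmatory standing.
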